10.2 Expectedness

An expected adverse reaction is an adverse reaction, the nature or severity of which is consistent with the applicable product information (Investigator’s Brochure for an CHF 718 pMDI or US-FDA approved Product Information for QVAR®), otherwise it is considered unexpected.

Reports which add significant information on specificity or severity of a known, already documented serious adverse drug reaction constitute unexpected events. For example, an event more specific or more severe than described in the Investigator's Brochure would be considered as "unexpected". Examples of such events are: (a) acute renal failure as a labeled ADR with a subsequent new report of interstitial nephritis and (b) hepatitis with a first report of fulminant hepatitis. In the event an exacerbation is interpreted as due to lack of efficacy, it should not be classified as drug related.

10.3 Intensity of Adverse Event

Each Adverse Event must be rated on a 3-point scale of increasing intensity:

- **Mild:** The event causes a minor discomfort, or does not interfere with daily activity of the subject, or does not lead to either modification of test treatment dosage or establishment of a correcting treatment.
- **Moderate:** The event perturbs the usual activity of the subject and is of a sufficient severity to make the subject uncomfortable. The event leads to a diminution of dosage of the test treatment, or a temporary interruption of its administration or to the establishment of a correcting treatment.
- **Severe:** The event prevents any usual routine activity of the subject and causes severe discomfort. It may be of such severity to cause the definitive interruption of test treatment.

10.4 Causality Assessment

The following "binary" decision choice will be used by the Investigator to describe the causality assessment:

- Reasonable possibility of a relatedness
- No reasonable possibility of relatedness

The expression "reasonable possibility of relatedness" is meant to convey, in general, that there are facts (evidence) or arguments meant to suggest a causal relationship.

The Investigator will be asked to consider the following before reaching a decision on causality assessment:

- Time relationship between study drug intake and event's onset;
- Dechallenge (did the event abate after stopping drug)?;
- Rechallenge (did the event reappear after reintroduction)?;
- Medical history;
- Study drug(s);
- Mechanism of action of the study drug;
- Class effects;
- Other treatments-concomitant or previous;
- Withdrawal of study drug(s);
- Lack of efficacy/worsening of existing condition;
- Erroneous treatment with study drug (or concomitant);
- Protocol related process.

10.5 Action taken with the study drug due to the AE

- Dose not changed
- Drug withdrawn
- Drug interrupted
- Not applicable
- Unknown

10.6 Other actions taken

- Specific therapy/medication
- Concomitant procedure
- Not applicable

10.7 Outcome

Each Adverse Event must be rated by choosing among:

- Recovered/resolved
- Recovering/resolving
- Not recovered/not resolved
- Recovered with sequelae/resolved with sequelae
- Fatal
- Unknown

10.8 Recording Adverse Events

All Adverse Events occurring during the course of the study must be documented in the Adverse Event page of the electronic Case Report Form (eCRF). Moreover, if the Adverse Event is serious, the Serious Adverse Event Form must also be completed.

It is responsibility of the Investigator to collect all adverse events (both serious and non-serious) derived by spontaneous, unsolicited reports of subjects, by observation and by routine open questionings.

The recording period for Adverse Events is the period starting from the Informed Consent signature until the subject's study participation ends.

Clinically significant abnormalities detected at Visit 1 not due to a pre-existing condition or clinically significant changes at the following visits in the medical opinion of the investigator must be reported as adverse events in the eCRF.

If a clinically significant abnormal laboratory finding or other abnormal assessment meets the definition of an AE, then the AE eCRF page must be completed, as appropriate. A diagnosis, if known, or clinical signs and symptoms if diagnosis is unknown, rather than the clinically significant abnormal laboratory finding, should be reported on AE eCRF page. If no diagnosis is known and clinical signs and symptoms are not present, then the abnormal finding should be recorded.

For pharmacovigilance purposes, all SAEs should be followed-up in order to elucidate as completely and practically as possible their nature and/or causality until resolution of all queries, clinical recovery is complete, laboratory results have returned to normal, stable condition is reached or until the subject is lost to follow-up. Follow-up may therefore continue after the subject has left the study. In this case, the follow-up will continue with no timelines for related SAEs, while for unrelated SAEs the type and extent of follow-up undertaken will be determined for each individual case and will depend upon the nature (e.g. events with poor prognosis or which do not resolve), severity and medical significance of the event.

10.9 Reporting Serious Adverse Events to Chiesi

The Investigator must report all Serious Adverse Events to the [REDACTED] Safety Contact listed below within 24 hours of awareness. The information must be sent by providing the completed Serious Adverse Event form. At a later date, the [REDACTED] Safety Contact will report all information to Chiesi Global Pharmacovigilance, the Clinical Project Manager and the Clinical Research Physician.

Name and Title	Telephone no.	Fax no.	E-mail
[REDACTED], MD Medical Safety Officer	[REDACTED]	[REDACTED]	[REDACTED]
[REDACTED] Global Pharmacovigilance Operation Specialist Global Pharmacovigilance, Chiesi Farmaceutici S.p.A	[REDACTED]	[REDACTED]	[REDACTED]

- Reporting of SAEs from the investigator site is from the time of subject's signature of informed consent and until the subject's study participation ends. After this date, even if no active monitoring of subjects is required, SAEs occurring to a subject should be reported if the investigator becomes aware of them.
- Up to the closure of the site, SAE reports should be reported to the [REDACTED] Safety Contact. New serious adverse event occurring after the site is closed should be reported directly to the Chiesi Safety Contact.

10.10 Reporting Serious Adverse Events to Regulatory Authorities/Ethics Committees/IRB

The Sponsor or designated CRO will report adverse events to the regulatory authorities in compliance with the timelines and standards of reporting according to local regulations (Guidance for industry and Investigators-Safety Reporting Requirements for INDs and BA/BE studies, December 2012). All suspected unexpected serious adverse reactions (SUSARs), which occur with the investigational medicinal product or marketed active comparator, within or outside the concerned clinical trial, will be reported by the Sponsor or designated CRO to regulatory authorities, as required, as well as to the Investigators and Central IRB, if applicable, by MedWatch/CIOMS form. The Investigator (or Sponsor/CRO where required) must inform the IRB per Sponsor instruction upon receipt of the SUSAR notification. An IND and/or NDA Safety Report will be submitted to regulatory authorities unblinded. Participating Investigators and IRB will receive a blinded IND Safety Report, unless otherwise specified.

With regard to regulations in force for Pharmacovigilance, the Investigator must fulfil his/her obligation according to the law in force.

10.11 General Notes

- In case of death, a comprehensive narrative report of the case should be prepared by the Investigator and sent to the [REDACTED]/Chiesi Safety Contact together with the Serious Adverse Event form, retaining a copy on site.
- If an autopsy is performed, copy of the autopsy report should be actively sought by the Investigator and sent to the [REDACTED]/Chiesi Safety Contact as soon as available, retaining a copy on site.
- In case of pregnancy, the subject will be immediately withdrawn from the study and she will be followed with due diligence until the outcome of the pregnancy is known. The pregnancy must be reported by the investigator within 24 hours by fax/e-mail/via Monitor to the [REDACTED]/Chiesi Safety Contact using the paper Pregnancy Report Form. The [REDACTED] Safety Contact will inform Chiesi of the pregnancy within one working day of being notified.

The first two pages of the Pregnancy Report Form should be completed by the investigator with all the available information and sent to the [REDACTED]/Chiesi Safety Contact. The third page will be completed as soon as the investigator has knowledge of the pregnancy outcome, together with a follow-up of the first two pages, if necessary (e.g. an update in the medications received during pregnancy by the mother). If it meets the criteria for immediate classification of a SAE (e.g. spontaneous or therapeutic abortion, stillbirth, neonatal death, congenital anomaly, birth defect) the Investigator should follow the procedure for reporting SAEs.

- If it is the partner, rather than the subject, who is found to be pregnant, the same procedure regarding pregnancy reporting is to be followed and the Pregnancy Report Form should be completed.
- If the pregnancy is discovered before taking any dose either of study drug or of the run-in ICS/rescue medication, the pregnancy does not need to be reported; it is only required that the subject is immediately withdrawn from the study.

11. DATA MANAGEMENT

An electronic CRF (eCRF) will be filled-in by the Investigator and/or his/her designee.

All subjects who sign the informed consent will be entered into the database. For subjects who are screened but not randomized, a minimum set of information is required: date of informed consent signed, demography, assessment of inclusion/exclusion criteria when applicable, primary reason for not continuing, prior medications, adverse events and concomitant medications, if any.

Subject's questionnaire (ACQ) answers will be databased.

Front-end edit checks will run at the time of data collection and back-end edit checks will be used by the Data Manager to check for discrepancies and to ensure consistency and completeness of the data.

Medical history, Concomitant Procedures and Adverse Events will be coded using the MedDRA dictionary; medications will be coded using the WHO Drug dictionary and Anatomical Therapeutic Chemical classification (ATC).

External data (IRT, Spirometry, e-diary, Laboratory) will be processed centrally and reconciled against data recorded in the eCRF as part of cleaning activities. After cleaning of data, a review

meeting will be held to determine the occurrence of any protocol violation and to define the subject populations for the analysis. Once the database has been declared to be complete and accurate, it will be locked, the randomization codes will be opened and the planned statistical analysis will be performed. Only authorised and well-documented updates to the study data are possible after database lock.

At the study conclusion, a complete copy of the study data will be created for archival purposes at Chiesi. The investigators will receive copies of the patient data for retention at the investigational sites.

12. STATISTICAL METHODS

12.1 Sample Size

The sample size has been calculated to evaluate the superiority of CHF 718 pMDI at different doses over placebo in terms of change from baseline in pre-dose morning FEV₁ at Week 8.

A total of 495 evaluable subjects (99 per group) will provide 80% power to detect a mean difference of 200mL between each dose of CHF 718 pMDI and placebo at a two-sided significance level of 0.0167, assuming a standard deviation of 430mL.

Since three dose levels will be tested, the Edwards and Berry method will be used to control the family-wise Type I error rate at the 0.05 (two-sided) level. In the sample size calculation, the Bonferroni adjustment of the significance level has been taken into account ($0.0167 = 0.05/3$). This will ensure the required power for each test, since the Edwards and Berry method is uniformly more powerful than the Bonferroni procedure.

Considering a non-evaluable rate of 15%, a total of approximately 585 subjects (117 per group) will be randomized.

12.2 Populations for analysis

- **Safety population:** all randomized subjects who receive at least one dose of study drug.
- **Intention-to-Treat population (ITT):** all randomized subjects who receive at least one dose of the study drug and with at least one available evaluation of efficacy (primary or secondary efficacy variables) after the baseline.
- **Per-protocol population (PP):** all subjects from the ITT population without any major protocol deviation (i.e., wrong inclusions, poor compliance, non-permitted medications). Exact definition of major protocol deviations will be discussed by the study team during the blind review of the data and described in the Data Review Report.

Since the superiority of CHF 718 pMDI at different doses over placebo will be tested, the primary efficacy analysis will be based on the ITT population. The primary efficacy analysis will be also performed on the PP population for sensitivity purposes.

The secondary efficacy variables will be analysed in the ITT population.

The safety variables will be analysed in the Safety population.

In case of deviation between randomized treatment and treatment actually received, the treatment actually received will be used in the safety analyses (i.e. an as-treated analysis will be performed).

12.3 Statistical analysis

A detailed statistical analysis plan will be described in a separate document. The plan might be reviewed and updated as a result of the blind review of the data and will be finalized before breaking the blind.

12.3.1 Descriptive Statistics

Descriptive statistics will be provided in summary tables by treatment group according to the type of variable summarized.

Descriptive statistics for quantitative variables will include n (the number of non-missing values), mean, SD, median, minimum and maximum values.

Categorical variables will be summarized by using frequency count and percent distribution.

12.3.2 Missing data

- For the primary efficacy analysis, a linear mixed model for repeated measures will be used to handle missing data. Under the Missing At Random (MAR) assumption, this model provides an unbiased estimate of the treatment effect that would have been observed if all subjects had continued on treatment for the full study duration. This approach addresses efficacy (or de jure) hypotheses, estimating the causal effects of the initially randomized drug if taken as directed (in contrast with effectiveness, or de facto, hypotheses, evaluating the effect of the drug as actually taken).[\[77\]](#) The efficacy estimand is considered appropriate in the context of a phase II study aiming at characterising dose-response.[\[78\]](#)[\[79\]](#)[\[80\]](#)
- If one of the spirometry measurements at 45 min and 15 min pre-dose is not available, then the non-missing measurement will be taken as the pre-dose value. If no measurement is available, then the pre-dose value will be considered as missing.
- A minimum of 7 days with available measurements will be required for each inter-visit period (including run-in period) to consider the following variables as non-missing: average use of rescue medication, percentage of rescue medication-free days, daily asthma symptoms, and percentage of asthma symptom-free days, percentage of asthma control days, morning and evening PEF.
- For ACQ-7 questionnaire, the total score will be calculated only if all the scores derived from all the seven items are recorded.

Further details on dealing with missing data, along with the handling of possible outliers, will be described in the SAP. Other critical missing data, if any, will be discussed during the review of the data. Decisions will be fully documented in the Data Review Report.

12.3.3 Subject demographics and baseline characteristics

The following variables will be summarized by treatment group on the ITT population (and on the Safety or PP populations, if relevant): demographic characteristics, medical history and concomitant diseases, previous and concomitant medications, efficacy and safety parameters at screening and/or at baseline.

12.3.4 Primary efficacy variables

Change from baseline in pre-dose morning FEV₁ will be analysed using a linear mixed model for repeated measurements including treatment, visit, treatment by visit interaction, ICS dose before study (low/medium daily dose) and US regions as fixed effects, and the baseline value (average of the pre-dose FEV₁ measurements at Visit 2) and baseline by visit interaction as covariates. An unstructured covariance matrix will be assumed.

The adjusted means in each treatment group, the adjusted mean difference between treatments and their 95% two-sided Confidence Intervals (CIs) at Week 8 will be estimated by the model. The CIs and the p-values of the comparisons between each dose of CHF 718 pMDI and placebo at Week 8 will be adjusted for multiplicity. The adjustment will be based on the parametric simulation method by Edwards and Berry.[\[81\]](#) At each dose level, the superiority of CHF 718 pMDI over placebo will be demonstrated by a statistically significant difference (adjusted p-value < 0.05) favoring CHF 718 pMDI.

All the other comparisons between treatments will be performed as secondary efficacy analyses with no multiplicity adjustment.

12.3.5 Secondary efficacy variables

No multiplicity adjustment will be performed in the secondary efficacy analyses.

- For change from baseline in pre-dose morning FEV₁ at Week 4, the adjusted means in each treatment group and the adjusted mean differences between treatments at Week 4 will be estimated with their 95% CIs and p-values by the same model used for the primary efficacy analysis.
- Change from baseline in pre-dose morning FVC at Week 4 and Week 8 will be analysed using a similar model as the one used for the primary efficacy analysis.
- Change from baseline in ACQ-7 score at Week 4 and Week 8 will be analysed using a similar model as the one used for the primary efficacy analysis.
- Change from baseline to each inter-visit period in average use of rescue medication, in percentage of rescue medication-free days, in daily asthma symptoms scores, in percentage of asthma symptoms-free days, in percentage of asthma control days and in morning and evening pre-dose PEF will be analysed using a similar model as the one used for the primary efficacy analysis. The inter-visit period will be considered instead of visit in the model. Comparison between treatments over the entire treatment period will also be derived from this model.

12.3.6 Safety variables

Adverse Events

All adverse events starting on or after the time of first study drug intake will be classified as Treatment Emergent Adverse Events (TEAEs). Any adverse event started after the informed consent signature and before the time of first study drug intake will be classified as pre-treatment adverse event. Pre-treatment adverse events will be listed only.

The number of TEAEs and the number and percentage of subjects who experienced at least one TEAE will be presented by treatment for all AEs, ADRs, serious AEs, serious ADRs, severe AEs, AEs leading to study discontinuation and AEs leading to death. Summaries will be presented overall and by system organ class and preferred term based on the MedDRA dictionary.

Vital signs

Vital signs (systolic and diastolic blood pressure) and their changes from baseline (Visit 2) will be summarized by treatment using descriptive statistics and the 95% CI of the mean.

ECG

12-lead ECG parameters (HR, QTcF, QRS and PR) and their changes from baseline (Visit 2) will be summarized by treatment using descriptive statistics and the CI of the mean (95% CI for absolute values and 90% CI for the changes from baseline).

The number and the percentage of subjects with a:

- QTcF >450ms (males only), >470ms (females only), >480ms (males only) and >500ms
- change from baseline (Visit 2) in QTcF >30ms and >60ms
- at post-baseline visit will be presented by treatment group.

Laboratory parameters

Shift tables from screening to the end of treatment, based on normal ranges, will be presented by treatment group for the laboratory parameters.

Mean change from baseline (Visit 2) to the end of treatment in 24-h urinary free cortisol and creatinine will be calculated with its 95% CI by treatment group.

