	
year, vital signs and training for the use of inhalers). Concomitant Medications and Adverse Events will be assessed. Dispensing of subject diary will be done. Eligible subjects will be provided with a container for the 24-h urine collection, to be returned to the site the day after completing the collection, 1-2 days before or on the date of their next visit (V2). This visit will be followed by a 14±2 day run-in period. Treatments that are disallowed by the protocol are to be discontinued at Visit 1, including current ICS (as monotherapy or as combination ICS/LABA). The subjects will be instead prescribed an equivalent daily dose of ICS as beclomethasone dipropionate (QVAR® 40 or 80µg/actuation) and this treatment regimen should remain stable for the entire run-in period. Subjects will receive rescue medication (albuterol) with instructions for “on demand” use for the entire study period.
 
▪ At randomization visit (Visit 2), inclusion/exclusion criteria, adverse events and concomitant medications will be reviewed. Eligibility recheck will be completed. Pre-dose vital signs and spirometry testing [FEV₁, FVC] will be performed. A 12-lead ECG, physical examination, urine pregnancy test will be performed, and training on the use of inhalers will be conducted. The ACQ will be assessed. The 24-h urine collection container will be collected from the subject if not already done, and shipped to a central laboratory for 24-h urine free cortisol and creatinine measurement. Eligible subjects will then be randomized to one of the treatment groups and will receive the 1st dose of study drug under medical supervision. The subjects will then leave the clinical center and will be instructed to return in 4 weeks.▪ At Week 4 (Visit 3) subjects will undergo a physical examination, urine pregnancy test, concomitant medications review, adverse events, study drug dispensation and vital signs assessment. Study drug will be returned and accountability will be performed. Pre-dose spirometry testing (FEV₁, FVC) will be performed and ACQ will be assessed. Subjects will be provided with a container for the 24-h urine collection, to be returned to the site the day after completing the collection, 1-2 days before or on the date of their next visit (V4). The subject will be instructed to return to the clinical center in 4 weeks.▪ At Week 8 (Visit 4) subjects will come to the clinical center and will undergo a physical examination, hematology and blood chemistry, serum/urine pregnancy test and vital signs assessment. A 12-lead ECG will be performed. Concomitant medications and adverse events will be assessed. Pre-dose spirometry testing [FEV₁, FVC] will be performed. No administration of the study drug will take place at V4. The ACQ will be assessed. The 24-h urine collection container will be collected from the subject if not already done, and shipped to a central laboratory for 24-h urine free cortisol and creatinine measurement. Study drug will be returned and accountability will be done. Subject diary will be returned by the subject. After the last assessment a follow-up phone call will be scheduled with the subject.▪ At Week 9 (Visit 5): A safety follow up phone call will be performed by the investigator or designated staff no later than 1 week after the final visit (V4) or Early Termination Visit to check the status of unresolved AEs and to record any new AEs that may have occurred

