Hospitalization refers to a situation whereby an AE is associated with unplanned overnight formal admission into hospital, usually for purpose of investigating and/or treating the AE. Hospitalization for the treatment of a medical condition that occurs on an “elective” or “scheduled” basis or for a pre-existing condition that did not worsen during the study should not necessarily be regarded as an AE. Complications that occur during the hospitalization are AEs. If a complication prolongs hospitalization, the event is an SAE. Emergency room visits that do not result in a formal admission into hospital should be evaluated for one of the other seriousness criteria (e.g., life-threatening; persistent or significant disability or incapacity; medically significant).

- **Results in persistent or significant disability or incapacity.**

The term significant disability should be viewed as any situation whereby an AE has a clinically important effect on the subject’s physical or psychological well-being to the extent that the subject is unable to function normally.

- **Is a congenital anomaly or birth defect**

- **Is a medically significant adverse event**

This criterion allows for any situations in which important adverse events/reactions that are not immediately life-threatening or do not result in death or hospitalization may jeopardise the subject’s health or may require intervention to prevent one of the above outcomes.

Examples of such events are: intensive treatment in an emergency room or at home for allergic bronchospasm; blood dyscrasias or convulsions that do not result in hospitalization; or development of drug dependency or drug abuse.

Medical and scientific judgment should be exercised in deciding whether an event is serious because medically significant. Any suspected transmission via a medicinal product of an infectious agent is also considered a serious adverse reaction.

A **Non-Serious Adverse Event/Non-Serious Adverse Drug Reaction** is an adverse event or adverse drug reaction that does not meet the criteria listed above for a serious adverse event/serious adverse drug reaction.

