7.2.11 Safety Assessments

There are 5 sets of safety variables identified in the protocol. A description of each variable, and the timing of the recording of the information is presented below.

- 1: Treatment Emergent Adverse Events (TEAEs)

Three categories of AEs will be presented: Pre-Treatment, Treatment Emergent, and Post-Study. An AE will be classified as:

- pre-treatment AE: if AE starts before the first randomized study medication intake (AE onset date < date of first randomized study medication intake).
- Treatment emergent AEs (TEAEs): all adverse events starting on or after the first study drug intake, up to study completion/discontinuation. TEAEs are defined as AEs with date of first randomized study drug intake \leq AE onset date \leq date of study completion/discontinuation.
- post-study AE: if AE starts after the date of completion/discontinuation (AE onset date > date of completion/discontinuation).

Additional variables to define an adverse event include the following:

- Serious AE (SAE) is defined as any AE that has the question “Is the AE serious?” marked as “Yes” on the eCRF.
- ADR is defined as any AE that has the question “Is the AE Related to Study Drug?” marked as “Yes” on the eCRF.
- Serious ADR is defined as any ADR that are also SAE
- *Severe AE*, defined as any AE that has intensity marked as “Severe” on the eCRF.
- *AE leading to study drug discontinuation*, defined as a TEAE where the action taken on the eCRF is marked as “Drug withdrawn”.
- *AE leading to death*, defined as a TEAE where the outcome is marked as “Fatal” on the eCRF.
- *Relative day of AE onset*, defined as the AE onset date – Date of first study drug intake + 1 if the AE onset date is greater or equal to date of first study drug intake. For pre-treatment AEs, the relative day is defined as the AE onset date – Date of first study drug intake. Relative day will not be calculated in case of partial/missing date of AE onset.
- *Duration of AE*, defined as the AE end date – AE onset date + 1 when the AE is resolved. If the AE is not resolved, the duration is defined as study completion date – AE onset date + 1 and the duration will be reported as “>x” in the listing. AE duration will not be calculated in the case of a partial/missing date of AE onset.

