10.7.1 Adverse Events

As defined in the protocol, all AEs starting on or after the date of first study drug intake will be classified as a TEAE. Only TEAEs will be included in the tables. AE onset date will be taken into account when assigning AEs as *treatment emergent*. Pre-treatment AEs (AE onset date < date of first randomized study drug intake) and post-study AEs (AE onset date > date of completion/discontinuation) will be included in the subject listings, and flagged, but will be excluded from other summaries.

The number of TEAEs, serious TEAEs, ADRs, serious ADRs, severe TEAEs, TEAEs leading to study drug discontinuation and TEAEs leading to death, and the number and the percentage of subjects experiencing TEAEs, ADRs, serious TEAEs, serious ADRs, severe TEAEs, TEAEs leading to study drug discontinuation and TEAEs leading to death will be summarized by treatment and overall.

The number and percentage of subjects with at least one AE and the number of AEs will be presented by SOC and PT by treatment and overall for treatment-emergent AEs, ADRs, serious TEAEs, serious ADRs, severe TEAEs, TEAEs leading to study drug discontinuation and TEAEs leading to death.

Subjects who have multiple events in the same system organ class (SOC) and preferred term (PT) will be counted only once in the subject counts.

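### Adverse events are classed as treatment-emergent by onset alone, so a run-in event that worsens after the first randomized dose can drop out of all the between-arm AE tables

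*Protocol*

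**What the plan says.** Protocol 12.3.6 (Adverse Events) sorts events by start time relative to first study drug intake. An event that began after consent and "before the time of first study drug intake will be classified as pre-treatment adverse event", and "Pre-treatment adverse events will be listed only".

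SAP 7.2.11 repeats the rule with the randomized drug as reference: "pre-treatment AE: if AE starts before the first randomized study medication intake". It operates this as a comparison of onset date with the date of first randomized intake. An AE leading to study drug discontinuation is "defined as a TEAE where the action taken on the eCRF is marked as" drug withdrawn, and an AE leading to death is likewise defined as a TEAE.

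SAP 10.7.1 confirms that onset date assigns the category and states: "Only TEAEs will be included in the tables". Pre-treatment events go to flagged listings and to no other summary.

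**The concern.** Treatment emergence is meant to separate what happened under randomized treatment from what was there before. A rule based only on onset does this for new events. It does not do it for an event already open at first dose that becomes worse afterwards, because the worsening happens on treatment but carries a run-in date.

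Such events are plausible in this design. AEs are recorded from consent (protocol 10.8). At Visit 1 subjects stop disallowed treatments, including any LABA, and change to an equivalent QVAR dose. They must still have an ACQ-7 score of at least 1.5 at Visit 2, when they move to placebo, one of three CHF 718 doses, or open-label QVAR. Safety and tolerability is a stated secondary objective, and the AE tables are where adverse events are compared between arms. At stake is whether those tables are complete for on-treatment harm, especially in the categories with few events.

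**Working it through.** The documents state no figure on this point, so the check is a trace of one event through the rules. Take an AE with onset on Day -4, mild in the run-in, which on Day 10 becomes severe and serious and leads to drug withdrawal.

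1. **Onset.** Protocol 10.8 starts AE recording at consent, so the event is entered with onset Day -4.
2. **Classification.** SAP 7.2.11 compares onset date with date of first randomized intake (Day 1). Day -4 is before Day 1, so the event is pre-treatment. Intensity, seriousness, action taken and outcome do not enter the comparison.
3. **Day 10, same record updated.** Onset is still Day -4, so the category does not change.
4. **Tables.**
   - TEAE, serious and severe tables: excluded, because SAP 10.7.1 counts treatment-emergent events only.
   - ADR and serious ADR tables: SAP 7.2.11 defines an ADR as any AE marked related, but the TEAE-only restriction in SAP 10.7.1 still applies.
   - Leading to discontinuation and leading to death: excluded by definition, since both must be TEAEs.
   - The event is therefore absent from Tables 14.3.1.1.1 to 14.3.2. It appears in Listing 16.2.7.1, and the withdrawal may be counted as a reason in the disposition summary (SAP 10.1).
5. **Day 10, new record opened.** Onset is Day 10, which is after Day 1. The event is a TEAE and enters every relevant table.

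The result turns on whether step 3 or step 5 is what sites do. The text that might settle this:

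- Protocol 10.8 requires changes that the investigator judges clinically significant at later visits to be reported as AEs. It is written for visit findings. It does not say that a worsened open AE gets a new record or a new onset date.
- Protocol 10.3 asks for one intensity rating per AE, and SAP 7.2.11 measures duration from onset to end date, or to study completion if unresolved. Both fit a single record carried to resolution.
- The worst-case allocation in SAP 7.2.11, with treatment-emergent first, covers only missing or incomplete dates. An AE with an uncertain onset thus defaults into the tables, while a known on-treatment worsening of a run-in event stays out.
- The re-allocation rules in SAP 10.8 do not mention AE reclassification.

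None of these requires step 5.

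**Size.** Arm size is 585 / 5 = 117. One subject is 1 / 117 = 0.0085, or about 0.85% of an arm. The documents give no run-in AE rate and no rate of later worsening, so no count of affected subjects can be derived.

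**The case against.** The strongest reply is that this is an unstated data-entry convention and not a faulty definition. The eCRF and the Data Management and Data Validation Plans are cited in the SAP but are not among the documents reviewed, and they may already tell sites to open a new record on worsening. Protocol 10.8 can be read that way, as can protocol 7.2.5 on ECG changes and 7.2.10 on laboratory findings after Visit 1. If sites do so, the onset rule works as written. This stands as a limit: the loss is conditional on record handling. It does not remove the point, because neither the protocol nor the SAP requires that handling.

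The second reply is that the worst cases are caught elsewhere, and much of it stands. A reader might infer that asthma deterioration after step-down disappears from the tables. A severe exacerbation after screening leads to permanent withdrawal and completion of an AE form (protocol 4.4). In the run-in it prevents randomization; on treatment it is naturally a new event with a post-dose onset. Lesser deterioration is compared between arms through FEV₁, ACQ-7, symptoms, rescue use and PEF.

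A reader might also infer that worsening local steroid effects at 800 µg/day are hidden. Oral candidiasis at screening or randomization is exclusion criterion 9 and is rechecked at Visit 2, so later thrush is a new event. It is the only local steroid effect for which the protocol plans a specific examination. Other events open at first dose remain possible, but they are a smaller group.

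**Conclusion.** The point holds in a limited form. The classification rule has no provision for worsening. If a site keeps one open record, a run-in AE that increases in intensity, becomes serious or ends study treatment after the first randomized dose is left out of the between-arm AE tables.

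The number of such subjects cannot be estimated and is probably small, given the Visit 2 eligibility checks. At about 0.85% of an arm per subject, the omission matters mainly for serious events, severe events and those leading to discontinuation. The primary efficacy analysis is untouched. The documents give no figures to show that any loss would differ by arm.

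Two stronger readings are not supported:

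- That such an event vanishes from all safety output. Blood pressure, ECG, laboratory shift and urinary cortisol tables are not filtered by AE onset. The event is listed and flagged, serious events are reported individually within 24 hours, and a withdrawal can be counted in the disposition table.
- That the plan treats worsening of a pre-existing condition differently from worsening of a run-in event. Protocol 10.1 does say that hospitalization "for a pre-existing condition that did not worsen during the study should not necessarily be regarded as an AE", but that sentence governs when a hospitalization counts as an AE, not which AEs are treatment-emergent.

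**What to change.** In protocol 12.3.6 and SAP 7.2.11 and 10.7.1, define a TEAE as an AE that (a) starts on or after the first randomized study drug intake, or (b) started earlier and, on or after that intake, increases in intensity, becomes serious or leads to study drug withdrawal.

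Add an eCRF completion instruction that such a change is entered as a new AE with its own onset date and that the run-in record is left as it was. The SAP's AE derivations use no date of worsening, so the new record is what makes limb (b) workable with the existing programs.

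Before unblinding, review the AEs ongoing at first dose against this rule and document the decisions in the Data Review Report. Protocol 12.3 already allows the SAP to be updated after blind review and before the blind is broken. If the definition cannot be changed, the minimum is a by-arm table of pre-treatment AEs that worsened, became serious or led to withdrawal after randomization.

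The cost is wording in two documents, one data-entry instruction and a short blinded review. TEAE counts may rise slightly.
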